## Project Summary

This University of Wisconsin Center for Tobacco Research and Intervention (UW-CTRI) study is designed to assess whether completely electronic, HIPAA-compliant, EHR-based, closed-loop referrals for tobacco cessation (eReferral) from primary care clinics to a state telephone tobacco quitline can increase the number/percentage of adult tobacco users receiving evidence-based tobacco dependence treatment when compared to paper-based faxed (Fax to Quit). We will also address the rate that referred smokers quit, whether they were referred via eReferral or Fax to Quit.

### 9/19/2017 Amendment Request

We propose changing three aspects of the currently approved protocol. All proposed changes pertain to the SmokefreeTXT electronic referral pilot substudy. First, we propose expanding the horizon for patient-selected target quit days from 14 to 30 days in the future, to reflect a change made by SmokefreeTXT and to ready SmokefreeTXT eReferral for integration with quitline eReferral in the future. Second, we seek to allow clinics to have greater flexibility in deciding which clinic staff roles/members should offer SmokefreeTXT eReferral. We are proposing this change because clinic leaders and staff have indicated that having staff who conduct vital sign assessment and place patients in clinic rooms be the primary conduit of SmokefreeTXT eReferral would be better for clinic workflow. This change affects one skip pattern in the post-SmokefreeTXT eReferral clinic staff survey, but does not affect the content, risks, or benefits associated with that survey. Finally, we seek permission to expand beyond primary care to specialty care clinics, at the request of specialty care clinics eager to implement SmokefreeTXT eReferral. These administrative changes will not affect study risks and may help to extend the reach of SmokefreeTXT by allowing more patients to engage in this evidence-based treatment to help them stop smoking.

### 2/28/2017 Amendment Request

## Project Summary

We would like to extend the scope of the project to include a pilot examination of the feasibility and effectiveness of eReferral to SmokefreeTXT, a text-messaging service for smokers trying to quit sponsored by the National Cancer Institute that is currently available to all Americans, without fees. Like the telephone tobacco quitline, SmokefreeTXT is an evidence-based smoking cessation support service that can be used to extend treatment provided by healthcare providers via referral. We believe it is important to evaluate eReferral to this text-based service as a potential complement or alternative to the quitline telephone counseling service. Fewer than 50% of those referred to the quitline accept counseling services and scheduling live calls is a challenge. SmokefreeTXT is an automated program that pushes out quitting coaching and support messages multiple times per day that users can access whenever they check their phones. In addition, SmokefreeTXT offers on-demand support regarding urges to smoke, smoking slips (i.e., cigarettes smoked during the quit attempt), and negative moods, in real-time. Although the quitline is also available for additional support, this is typically not in real time and usually requires calls back. As such, we expect that SmokefreeTXT may have a higher rate of

engagement that Quitline services and believe it is important to evaluate SmokefreeTXT independent of Quitline referral.

As in the initial protocol, we seek to evaluate the extent to which electronic, HIPAA-compliant, EHR-based, closed-loop referral for tobacco cessation support (in this case, via text messages rather than live phone calls) from primary care clinics can increase the number/percentage of adult tobacco users receiving evidence-based tobacco dependence treatment. In this amendment, we seek to use up to three clinics in the Gundersen healthcare system as eReferral sites in which to evaluate eReferral to SmokefreeTXT alone (without concomitant eReferral to the quitline). We seek to evaluate the eReferral to SmokefreeTXT by examining uptake rates relative to a baseline period in 1-3 clinics (rather than relative to clinics randomized to a control condition) and by examining continuing engagement and self-reported abstinence rates using deidentified data obtained from the SmokefreeTXT vendor six weeks after referral.

We would also like to note that the name of one of the health care systems in which the eReferral to the Quitline is being compared to fax-to-quit referral to the Quitline has changed due to a merger. The system formerly known as Wheaton Franciscan is now called Ascension Wisconsin. This change has been noted throughout this document.

Finally, we would like to add two survey items to the post-eReferral survey completed by clinic staff at the end of the Quitline eReferral study (see Appendix A) to assess how healthcare providers are introducing the eReferral to patients. We have found considerable heterogeneity across providers and clinics in response to eReferral and we want to assess whether there is similar heterogeneity in the ways providers report introducing the Quitline and link this to rates of eReferral and Quitline service engagement across clinics (not specific providers) in our analyses of Quitline referral methods

## **Research Protocol**

### **Closed-Loop Telephone Tobacco Quitline eReferral**

ABBREVIATIONS	
QL	Quitline
WTQL	Wisconsin Tobacco Quit Line
EHR	Electronic Health Record
F2Q	Paper Fax to Quit Referral to the Quitline
eReferral	EHR-based electronic referral to the Quitline
UW-CTRI	University of Wisconsin Center for Tobacco Research and Intervention
GHS	Gundersen Health System
AW	Ascension Wisconsin Healthcare
Epic	Epic Systems Corporation
Optum	Formerly Alere Wellbeing/Wisconsin Tobacco Quit Line Vendor
MA	Medical Assistant
BPA	Best Practice Advisory
IRB	Institutional Review Board
CDS	Clinical Decision Support
CY	Calendar Year

#### **Specific Aims:**

This UW-CTRI study is designed to assess whether completely electronic, EHR-based, closed-loop referrals for tobacco cessation (eReferral) from primary care clinics to a state telephone tobacco quitline can increase the number/percentage of adult tobacco users receiving evidence-based tobacco dependence treatment when compared to paper-based, manual fax referrals.

2/28/2017 Amendment: The specific aim of this extension of the protocol is to evaluate the extent to which electronic, closed-loop eReferral to SmokefreeTXT in up to 3 primary care clinics engages patients who smoke in the program, retains these individuals in the 6-week duration of the program, and helps them to quit smoking as assessed via self-report at the end of the 6-week program.

**Primary Aim 1:** To evaluate the rates of referral of tobacco users visiting primary care clinics to the WTQL, comparing those who were referred via an EHR-based electronic referral system vs. those referred via a manual paper fax referral system. Analyses will address the change in referrals from pre- to post-intervention and the trajectory of referral post-intervention per clinic.

**Primary Aim 2:** To evaluate the rates of quality referrals of tobacco users visiting primary care clinics to the WTQL, comparing those who were referred via an EHR-based electronic referral system vs. those referred via a manual paper fax referral system (quality referrals are defined as ones that result in individuals who enroll in and receive WTQL counseling and/or medication treatment services). Analyses will address the change in referrals from pre- to post-intervention per clinic.

2/28/2017 Amendment: The primary aim of the SmokefreeTXT eReferral project is to examine uptake (initial enrollment), retention (continuing engagement through the end of the 6-week program), and effectiveness (in terms of abstinence 6-weeks after the target stop-smoking date) of eReferral to SmokefreeTXT among primary care patients referred by clinic staff during clinic visits.

**Secondary Aim 1:** To examine variation in referral rates across clinics to test the hypothesis that the eReferral system will result in greater consistency in referral in addition to higher rates of referral. Nonquantitative methods will be used to understand the sources of variation.

**Secondary Aim 2:** To evaluate smoking abstinence rates of tobacco users who were referred to and accepted services from the WTQL, comparing those who were referred via an EHR-based referral system vs. those referred via a manual paper fax referral system. Analyses will address 7-day point prevalence smoking outcomes at 4-months after participant registration with the WTQL and will reflect per clinic rates.

**Secondary Aim 3:** To assess clinician and staff satisfaction with the eReferral and paper F2Q systems.

2/28/2017 Amendment: A secondary aim of the SmokefreeTXT eReferral project is to gather information about the process of implementing eReferral to SmokefreeTXT in primary care clinics, particularly regarding clinic staff implementation of and satisfaction with the SmokefreeTXT eReferral system.

#### **Background:**

The move from the current system of paper-based fax referrals (F2Q) to telephone tobacco quitlines to fully electronic EHR-based referrals (eReferrals) is progressing at a very slow rate – especially when

compared to the rapid advances of other electronic health record (EHR) tools such as ePrescribing. This research is designed to compare the functionality and effectiveness of electronic versus paper-based faxed referrals of outpatients to a telephone tobacco quitline.

#### The Paper Fax-to-Quit Tobacco Quitline Referral System

A paper *Fax-to-Quit (F2Q)* program for the Wisconsin Tobacco Quit Line (WTQL) was developed in 2003 by UW-CTRI as a mechanism to provide evidence-based tobacco cessation treatment to clinic and hospital patients. This system was developed in response to health system requests to more efficiently link their patients to the WTQL (see Figure 1 for F2Q workflow description). Once a healthcare system requests implementation of a F2Q program, UW-CTRI Outreach staff travel to the clinic or hospital to train staff on using the program and provide necessary materials (e.g., clinic-specific F2Q referral form – Figure 2). Utilizing F2Q is relatively simple but requires a number of steps. First, staff have to query patients regarding their tobacco use status. Staff then describe WTQL services (tobacco cessation counseling and nicotine replacement therapy) to the identified tobacco user and ask if the patient is interested in receiving such services. If the patient agrees and provides written permission, staff then manually complete a paper F2Q form that includes contact information and best times for the WTQL to call the patient. The form is then manually faxed by a clinic staff person to the WTQL; the WTQL then attempts to contact the patient within 48 hours and deliver WTQL treatment services. Depending on the clinic, different staff members assume responsibility for these different tasks. Finally, the WTQL faxes back to the referring clinic/provider (not to the patient's chart) a form describing the outcome of the referral, including whether their patient was reached, if s/he agreed to receive services, and which services were provided. Clinics are encouraged to enter such QL treatment information into the patient's EHR (via scanning or manually), but few clinics report doing so. Since 2003, approximately 1,000 healthcare settings (clinics, hospitals) in Wisconsin have implemented a F2Q program, with 221 active (referred at least one patient to the WTQL) in 2014 (many clinics that implement F2Q don't continue to use it, in part due to the cumbersome operational requirements). In 2014, these 221 active sites referred a total of 2,420 patients to the WTQL, averaging 11 referrals per clinic per year (WTQL data). Of the patients fax referred, 41% enrolled in WTQL services.

2/28/2017 Amendment: No such fax-to-quit referral system currently exists for SmokefreeTXT, although information about the service is provided via handouts or after-visit summaries in some clinics. Indeed, there is no systematic referral mechanism to SmokefreeTXT in the clinics under study or those that might disseminate eReferral to SmokefreeTXT, should it be found to be effective. As such, there is a need for pilot work to determine the feasibility and uptake of a referral process for SmokefreeTXT. In light of the challenges and low enrollment rates observed with a paper-based process in the fax-to-quit program for referral to the Quitline, we are electing to use EHR technology to implement an eReferral process for SmokefreeTXT.

#### The eReferral Quitline Referral System

In an effort to take advantage of the recent wide scale implementation of electronic health record (EHR) technology in healthcare settings in Wisconsin and nationwide, UW-CTRI, in collaboration with Epic Systems Corporation (Epic), health systems, and the Wisconsin Tobacco Quitline vendor (Optum) developed a new electronic quitline referral system (eReferral) (see Figure 3 for eReferral workflow description). This new system is designed to more efficiently and effectively refer patients who smoke and visit a healthcare facility to the WTQL. Specifically, during every patient visit, the EHR already prompts the clinic Medical Assistant (MA) or Roomer (the clinic staff person who typically transports the patient from the waiting area to the examination room and collects key information prior to the clinician seeing the patient, e.g., current medications, vital signs, allergies) to inquire about tobacco use as part of

the standard EHR workflow – a near-universal process as a result of the Federal meaningful use of EHRs incentive program and other regulatory requirements. The MA’s documentation of tobacco use activates a “Best Practice Advisory” (“BPA” - an Epic EHR-tool to guide evidence-based clinical interventions) that electronically prompts the clinician to offer tobacco quitline services (see Figures 3 and 4).

The BPA gives the clinician the choice of selecting a WTQL referral *order* or documenting that the *patient declined* a referral to the WTQL. If the patient indicates an interest in receiving WTQL services, the clinician “accepts” the BPA which takes him/her to the *eReferral order*, which is automatically populated with the patient’s name and contact information, and presents options for the clinician to indicate optimal times for the WTQL to call the patient. The eReferral is then sent to Optum, the WTQL vendor (Figure 4), in real-time when the provider clicks “Place Order.” The exchange of patient information in both directions (closed-loop) between the healthcare system and the WTQL is done via Health Level 7 version 2 (HL7v2) standard messaging. The data sent to the WTQL will be in a general outgoing order message (ORM in HL7v2), and the WTQL will return an unsolicited observation message (ORU in HL7v2) and a pharmacy encoded order (RDE in HL7v2).

Once the WTQL receives an eReferral, they attempt to contact the patient and provide cessation services exactly as occurs with the paper fax referral described above. Once the WTQL completes treatment or exhausts the five attempts to reach the patient, the quitline electronically sends the WTQL treatment data back to the patient’s EHR, which automatically populates the patient’s EHR in two places – data on patient contact, counseling provided, and quit date are saved as a “referral outcome note” (Figure 5), while provision of over-the-counter nicotine replacement medication (including the medication start-and end-dates based on the quit date) is documented in the patient’s medication list (Figure 5).

2/28/2017 Amendment: The workflow for eReferral to SmokefreeTXT will mimic that of eReferral to the Quitline almost exactly. Medical Assistants or Roomers will be responsible for assessing smoking status and recording this in the EHR, in accordance with current clinic practices and standards of care. As with the Quitline eReferral, documentation of current smoking status for a patient will activate a BPA that will alert the clinic staff to the smoking status of the patient and will prompt the clinic staff person to offer referral to SmokefreeTXT to the patient. Clinic staff will record in the BPA whether the patient accepted referral or declined the service. If the patient accepts, that clinic staff member will also need to record a target stop smoking day in the next 30 days. If the patient accepts the service, a SmokefreeTXT eReferral order will be populated and queued for clinician review and confirmation. SmokefreeTXT eReferral orders placed by clinic staff will be sent to ICF International, the vendor that implements SmokefreeTXT, in real-time, using Health Level 7 Version 2 general outgoing order message (ORM in HL7v2). Six weeks after the target stop-smoking date, ICF International will send an unsolicited results message (ORU in HL7v2) that will go to the patient’s providers EHR inbox and the patient’s record. Because SmokefreeTXT does not provide medications to users, it will not be necessary to update the patient’s medication list as it was for eReferral to the Quitline. Clinic staff will be instructed to offer other tobacco dependence treatments in accordance with best practices, as they see fit. This means that clinic staff may refer some patients to the Quitline (via fax, handout, or both), prescribe stop-smoking medications, refer patients to an in-clinic or in-system specialist, and/or provide brief counseling. This is in keeping with the intent of the project, which is to evaluate eReferral to external resources as treatment extenders rather than treatment substitutes.

## **Methods:**

**Methods Overview:** Following UW Institutional Review Board (IRB) approval, the study will take place in primary care clinics (general internal medicine/family practice) that are part of Ascension Wisconsin Healthcare (AW) and Gundersen Health System (GHS). Each is an integrated healthcare delivery system located in southeastern Wisconsin (AW), and western Wisconsin, northeastern Iowa and southeastern Minnesota (GHS) respectively. AW includes approximately 50 primary care clinics with over one million outpatient visits annually. GHS includes 27 primary care clinics with over one million outpatient visits annually. Currently, some of these primary care clinics offer paper F2Q referrals to the WTQL for patients who use tobacco and want to quit. The target population for the study will comprise adult (18 and older) patients who use tobacco, want to quit, and seek primary care clinical services during the study period. In consultation with each system, about 26 clinics will be selected for participation in the study, one pilot clinic per system to test the new eReferral software. The remaining clinics, about 12 clinics from each system, will be randomized to the two study conditions (see below).

2/28/2017 Amendment: Following IRB approval of this amendment, the study will take place in up to 3 clinics in the Gundersen Health System. As in the existing protocol, the target population will be adult (age 18 and older) patients served at these clinics during the study period who smoke combustible cigarettes and are willing to set a target stop-smoking date in the period required by the referral service (in this case, the quit date must be within 30 days). There will be no control clinics and no randomization of clinics to condition in this pilot project.

## I. Methods for Evaluating the eReferral Mechanism

The study will include three phases (see Table 1):

- 1) The Preparation Phase (3 months): 24 clinics (12 clinics/system) are to participate in the randomized clinical trial. Clinics will meet inclusion criteria (see below), and generate baseline rates of manual paper fax referral of adult tobacco users to the WTQL. These will be calculated for the prior 6-12 months, and the 24 clinics that will participate in the clinical trial will be randomized to two different WTQL referral mechanisms (twelve to use the manual F2Q mechanism, and twelve to transition to the eReferral mechanism). Also during this phase, the eReferral procedures and technology will be tested in one clinic within each system for one to three months. The technology will be adapted as needed. These pilot clinics will not be involved in the research.
- 2) The Study Implementation Phase (12 months): Staff in all 24 clinics will receive a baseline 30 minute in-person training, regarding either the paper or electronic referral to the WTQL (based on their randomization). While some of the clinics randomized to the paper referral system will have already received training on this referral mechanism at some time in the past (when the system was implemented in that clinic or refreshed), we will provide a refresher training on F2Q referral for all clinics in this condition consisting of about the same amount of time as used in the eReferral training. An UW-CTRI Outreach Specialist will lead all trainings and a member of the research team will also be present. All Medical Assistants, Nurses, Clinician Providers (physicians, nurse practitioners, and physician assistants), and Clinic Managers will be asked to attend the training. For any staff member who misses the initial training, a second training will be scheduled and data collected on the proportion of all staff who attended either of the trainings.

A UW-CTRI Outreach Specialist will provide additional support to all 24 participating clinics to encourage referrals to the WTQL modeled on typical clinical performance feedback activities. Specifically, this periodic support will include: 1) a one-week post-intervention launch, telephone or email check-in by UW-CTRI staff with both the Clinic Manager and the Physician Leader of each clinic, focusing on early challenges and problem solving as well as emphasizing the importance of systematically identifying tobacco users and referring (either via F2Q or eReferral) all appropriate patients to the tobacco quitline (“quality contacts”), 2) Monthly performance feedback will be shared with all staff and will include rates of F2Q or eReferrals from each clinic as well as data on the quality of the referral - the proportion of referrals that result in tobacco users who engage in quitline counseling (“quality contacts”). Specific performance feedback on the number of referrals and the number who accepted service will be provided for the clinic as a whole. Finally, 3) clinic staff will be provided with e-mail and telephone access to UW-CTRI staff who will be available to respond to questions or concerns about the F2Q or eReferral program.

At about one month after the launch of the intervention, all clinics will receive a refresher training (about 20 min) based on their randomized condition (F2Q vs. eReferral). Attempts will be made to piggy-back all trainings onto existing staff meetings. In total, rates of referral to the WTQL from all 24 clinics will be monitored for 6 months after the initial training. In this way we will compare the number and quality of quitline referrals between the six clinics randomized to the F2Q system and the six randomized to the e-Referral mechanism for receipt of WTQL treatment services.

2/28/2017 Amendment: This pilot SmokefreeTXT eReferral evaluation project will take place in 1-3 clinics (depending on clinic size, patient flow, and smoking prevalence in the clinics) over 12-17 months. This will include 2-4 months to finalize and troubleshoot the eReferral technological specifications with ICF International, Epic Systems, and Gundersen Health System Information Technology staff and then 6-9 months of testing of SmokefreeTXT eReferral engagement, retention, and effectiveness. Effectiveness testing will end 8 weeks after the end of eReferral implementation in each of the clinics, so eReferrals will end 8-11 months post-launch.

Evaluation and dissemination of results will occur over the next 2-4 months. In the host clinics, staff will be surveyed regarding their tobacco dependence treatment practices and attitudes and their knowledge of SmokefreeTXT prior to study launch. As in the existing Quitline referral protocol, an UW-CTRI Outreach Specialist and Gundersen IT trainer will provide training in SmokefreeTXT eReferral in a clinic staff meeting shortly before the EHR-enabled process goes live and will elicit feedback and provide additional training at a scheduled one-month follow-up staff meeting. The UW-CTRI Outreach Specialist will also be available to provide support to eReferral clinics upon clinic request, as needed.

- 1) The Evaluation Phase (6 months): Data will be analyzed, findings will be shared with the health system, and at least one manuscript describing the findings will be prepared and submitted for publication. 2/28/2017 Amendment: In the 2-4 month Evaluation Phase for the SmokefreeTXT eReferral pilot, data will be analyzed and results disseminated to the healthcare system, ICF International, and a peer-reviewed academic journal.

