2/28/2017 Amendment. As with eReferral to the telephone Quitline, eReferral to SmokefreeTXT will be a fully electronic, "closed-loop" referral in which the outcome of the referral is automatically fed back

into the patient's EHR 6 weeks after the target stop-smoking date. When a "Roomer" documents that a patient is currently a smoker, this will cue a Best Practice Advisory (BPA) to appear for clinic staff during the encounter. This BPA will guide clinic staff in the offer of SmokefreeTXT and allow them to document the patient response (acceptance or decline). If a patient consents to setting a quit day in the next 30 days, indicates that they have a text-capable phone, and accepts the referral, the provider will place an order for the text-capable phone to receive SmokefreeTXT messages. SmokefreeTXT will send terms of use (including a notice that text messaging fee rates may apply) and privacy practice information to the identified phone upon receipt of the eReferral. Patients have the option to stop receiving SmokefreeTXT messages at any time by texting "STOP" to SmokefreeTXT. Text messages may use patient cell-phone service plan minutes. Patients will be advised of this by SmokefreeTXT upon enrollment. Patient records in the EHR will be automatically update with the result of the eReferral 6 weeks after the target stop-smoking date (set at enrollment). This may be up to 10 weeks post-referral (as the target stop-smoking date could be set up to 30 days after eReferral) and will indicate whether the patient stayed enrolled, dropped out (by texting "STOP"), and reported any smoking in the past 7 days at the 6-week post-quit follow-up. No medications will be provided by SmokefreeTXT, so there will be no need to update the patient medication list in the EHR.

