2/28/2017 Amendment. For evaluation of eReferral to SmokefreeTXT, dependent variables will parallel those in the existing protocol for Quitline eReferral. The SmokefreeTXT vendor (ICF International) will send summary data regarding the number of eReferrals received and the number of patients engaged by clinic to study staff no less than monthly. These summary data will indicate how many eReferrals were received, how many were successfully enrolled in the program (i.e., who had a working number), how many of those enrolled dropped out by texting STOP to the program, and, finally, how many texted responses indicating no smoking vs. any smoking in the last 7 days 6 weeks post-target-quit date. Aggregate EHR data will be pulled from the health system at the end of the study to ensure that the number of eReferrals received by ICF International is consistent with the number of eReferrals sent, as recorded in the EHR. These EHR reports will also indicate the total number of patients seen, the total number of visits completed, the total number of patients who smoke seen, and the total number of visits completed by patients who smoke during the active eReferral evaluation period in each clinic, as well. This will be used to determine the rates of referral, engagement, and retention in SmokefreeTXT.

UW-CTRI will evaluate the principal dependent measures on the basis of rate of tobacco users referred to the WTQL/month, showing changes from the baseline to the post-intervention periods on the basis of percentage of tobacco user referral or contact status/tobacco user flow at each clinic. The public health importance of this research will be seen if the EHR-based program results in rates of referrals and contacts (and quality referrals and contacts) that are higher, more uniform, and more sustained across time, than are generated by the F2Q method. It is possible that changes in contact rates from the baseline period to the post-intervention period may reflect correlated secular changes or simply the

passage of time. Therefore, we will keep track of potentially relevant secular events. In addition, because the F2Q control and the EHR referral clinics will enter the study on the same time line, the occurrence of secular changes should not differentially affect the two conditions.

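### SmokefreeTXT pilot: effectiveness testing closes 56 days after eReferral ends, but the 6-week abstinence outcome can fall due 72 days after referral (minor)

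*Combined protocol and SAP*

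**What the plan says.** All of the text below is current text on the SmokefreeTXT pilot, in paragraphs marked as the 2/28/2017 Amendment.

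- **Close of testing** (Methods for Evaluating the eReferral Mechanism): "Effectiveness testing will end 8 weeks after the end of eReferral implementation in each of the clinics".
- **Quit-date horizon.** The Methods Overview says "in this case, the quit date must be within 30 days". The workflow under The eReferral Quitline Referral System has clinic staff "record a target stop smoking day in the next 30 days".
- **Outcome.** Specific Aims includes "effectiveness (in terms of abstinence 6-weeks after the target stop-smoking date" in the pilot's primary aim. Dependent Variables for Intervention Phase has the vendor report how many patients texted "no smoking vs. any smoking in the last 7 days 6 weeks post-target-quit date".
- **Time from referral to result** (Tobacco User Referral in eReferral Condition): "This may be up to 10 weeks post-referral (as the target stop-smoking date could be set up to 30 days after eReferral". The same paragraph ties the 6-week result to the date set at enrollment.
- **After testing** (Methods for Evaluating the eReferral Mechanism): "Evaluation and dissemination of results will occur over the next 2-4 months".
- **Length of eReferral.** The sentence that gives the 8-week close continues "so eReferrals will end 8-11 months post-launch". Table 1A gives 6-9 months for implementation, and the pilot paragraphs under Clinic Eligibility Requirements and Clinic Randomization give 6-9 months of active eReferral.

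**The concern.** An 8-week window cannot hold an outcome that the same document says may arrive 10 weeks after referral. Six-week abstinence is one of the three parts of the pilot's primary aim, and quit rates are to be reported by clinic in only one to three clinics.

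If the close is applied as a data cut-off, some late referrals have no abstinence result. They are not a random subset, because among late referrals they are the patients who chose the more distant quit dates. The plan does not say whether such patients would stay in the quit-rate denominator, be left out, or be counted as missing.

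**Working it through.** **Inputs.** Close of testing: 8 weeks = 56 days after eReferral ends. Maximum quit-date lead: 30 days. Follow-up from the quit date: 6 weeks = 42 days. Length of eReferral: 6-9 months, taken as 180 and 270 days.

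**1. Reproducing the plan's 8 weeks.** Latest due date = maximum lead + 42.
- With a 14-day lead: 14 + 42 = 56 days, exactly 8 weeks.
- With the current 30-day lead: 30 + 42 = 72 days, or 10.3 weeks.

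The 9/19/2017 amendment request records that the horizon was widened from 14 to 30 days, so the 8-week figure was probably not updated. That is only a likely explanation. The conflict lies within the current text and does not depend on it.

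**2. Shortfall.** 72 - 56 = 16 days. On the plan's own 10 weeks, 70 - 56 = 14 days.

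**3. Who would be affected if day 56 is a cut-off.** Take a patient referred t days before eReferral ends, with a quit date q days ahead. The outcome falls due q + 42 - t days after eReferral ends. It is lost only if q + 42 - t > 56, that is, if q - t > 14.

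**4. Share of referrals.** The documents give no distribution of quit dates, so this step assumes even referral flow and q uniform over 0 to 30 days.
- For a given t, the share lost is (16 - t)/30.
- Integrating over t = 0 to 16 gives (16 × 16/2)/30 = 128/30 = 4.27 days' worth of referrals.
- Over 6 months: 4.27/180 = 2.4%. Over 9 months: 4.27/270 = 1.6%.
- Check with whole-day leads of 1 to 30: 136/30 = 4.53 days, giving 2.5% and 1.7%.

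**5. Upper bound.** If every patient chooses day 30, all referrals in the last 16 days are lost: 16/180 = 8.9% and 16/270 = 5.9%.

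**6. Room in the timeline.** If the 2-4 month evaluation phase starts at day 56, its shortest form runs to 56 + 60 = day 116, well past day 72.

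**7. The 8-11 month clause.** Eight weeks is 56/30.44 = 1.8 months, so 6-9 months plus 8 weeks is 7.8-10.8 months. The 8-11 months therefore fits the end of effectiveness testing, whereas the sentence says it is when eReferrals end. This reading is an inference. As written, the clause conflicts with 6-9 months of eReferral. If eReferral did run 8-11 months (240 and 330 days), the 16-day shortfall would be unchanged and the central share would be 4.27/240 = 1.8% to 4.27/330 = 1.3%.

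**The case against.** The strongest reply is that nothing calls day 56 a data cut-off. The vendor's result message is automatic, vendor summaries come at least monthly, aggregate EHR data are pulled at the end of the study, and an evaluation phase of at least 2 months follows. On that reading every outcome arrives and nothing is lost. This stands, so a reader who infers that abstinence data will certainly be missing goes further than the documents do. It does not remove the contradiction. Specific Aims defines effectiveness as the 6-week abstinence result, so an end to effectiveness testing most naturally means an end to collecting it. Table 1A also lists data collection under implementation and not under evaluation.

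A reader might also infer that everyone referred in the last 16 days with a quit date more than 14 days ahead is lost. That overstates the group. Someone referred 10 days before the end with a quit date 20 days ahead falls due on day 20 + 42 - 10 = 52 and is captured. Under the same assumptions the wider group holds 16 × 16/30 = 8.53 days of referrals, twice the 4.27 that are affected.

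Finally, a reader might see a further error in the pilot's stated 12-17 month total. The documents do not support that: it is a planning range, its ends need not equal the sums of the phase extremes, and no result depends on it.

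**Conclusion.** The contradiction is real: the close of effectiveness testing falls 14 to 16 days before the last abstinence outcomes are due. The date arithmetic needs no assumption beyond the plan's own figures.

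The consequence is conditional and small. If day 56 is a cut-off, about 1.6-2.4% of referrals would lack the outcome over 6-9 months, on assumed even flow and uniform quit dates, with an upper bound of 5.9-8.9%. If it is not a cut-off, the loss is zero. Only the abstinence part of a descriptive pilot with no hypothesis test is touched, and the randomized comparison of eReferral with fax referral is unaffected. Severity is minor.

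**What to change.** - Reconcile the 8-week close with the 10 weeks stated under Tobacco User Referral in eReferral Condition. Set the close of effectiveness testing and the final vendor data pull at 72 days plus a few days for text replies, for example 11 weeks (77 days), after the last eReferral in each clinic. Day 72 is when the last outcome falls due, so a pull on that day leaves no time for a reply.
- If data must be pulled earlier, restrict the quit-rate analysis by referral date, to patients referred at least 72 days before the pull, and say so. Do not restrict it to patients whose 6-week point has passed: among late referrals that keeps near quit dates and drops distant ones.
- Correct the clause that has eReferrals ending 8-11 months after launch so that it agrees with the 6-9 months of eReferral stated elsewhere.

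The cost is 16 days (72 - 56) to 21 days (77 - 56) before the final pull, which the 2-4 month evaluation phase can absorb, plus a few words of editing. The 6-week assessment is already standard in the program, so patients and staff carry no added burden.
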